#### *12.4.1 Hypothesis*

The primary effectiveness objective will be assessed with the following hypothesis:

$$H_0: h_{\text{Control}}(t) = h_{\text{Treatment}}(t) \text{ for all } t \leq T \text{ years } H_A: \\ h_{\text{Control}}(t) \neq h_{\text{Treatment}}(t) \text{ for some } t \leq T \text{ years}$$

where  $h(t)$  is the hazard function (risk) of chronic treatment failure and  $T$  is the total study time.

#### **12.4.2 Performance Requirements**

If the hazard ratio for chronic treatment failure between the Treatment and Control only arms is less than one and the two-sided log-rank p-value is less than 0.05, it will be concluded that the pulmonary vein isolation and renal artery denervation procedure results in a higher rate of chronic treatment success.

Given the feasibility nature of this study and relatively small sample size, even if the pulmonary vein isolation and renal artery denervation procedure results in a clinically meaningful improvement in the rate of chronic treatment success (e.g. an absolute 10-15% higher chronic treatment success rate through 6 months), the log-rank test may not reach statistical significance ( $p < 0.05$ ).

This study is intended to provide data to support the design of a pivotal trial. The estimates of the chronic treatment success rate for each study arm can provide that data whether the log-rank test is statistically significant or not.

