#### **12.4.6 Sample Size**

There will be at least 78% power to test this objective provided at least 70 subjects undergo randomization.

The sample size calculation is based on the following assumptions:

- 1:1 randomization
- Constant randomization rate over 16 months
- Last enrolled subject followed through 6 months post-procedure
- 50% chronic treatment success in the PVI only arm versus 75% in the Treatment arm (equivalent to a hazard ratio of 0.415) through 6 months post-procedure
- Constant hazard ratio over all follow-up
- Cumulative alpha of 0.05. Any planned interim analyses will be constructed so that the overall Type I error of the study is no greater than 0.05.
- Constant attrition (dropout) of 5% per 6 months

The sample size calculation was performed in PASS 2008 using the log-rank (Lakatos) procedure. Accounting for a study attrition rate of up to 5% per 6 months ensures that the study will maintain the planned power of 78% in case attrition is higher than expected (approximately 1% per 6 months).

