## 12.8 Interim analysis

Interim analyses will be performed.

Two interim analysis of the primary effectiveness objective may be performed after 32 and 50 subjects have been randomized and completed their 6-month follow-up visits, respectively. Both the sponsor and the DMC will assess the results of the interim analyses of the primary effectiveness objective and based on this assessment, the sponsor may decide to stop enrollment.

Time Point of Interim Analyses of the Primary Effectiveness Objective	Cumulative Alpha	Boundary*	Pass/Fail Primary Effectiveness Objective
After 32 subjects were randomized and completed their 6-month visit	0.01	0.01	If a two-sided p-value $\leq 0.01$ , in favor of the treatment group, then the study passed the primary effectiveness objective
After 50 subjects were randomized and completed their 6-month visit	0.015	0.008	If a two-sided p-value $\leq 0.008$ , in favor of the treatment group, then the study passed the primary effectiveness objective
Final Analysis: After 70 subjects were randomized and completed their 6-month visit	0.05	0.04	If a two-sided p-value $\leq 0.04$ , in favor of the treatment group, then the study passed the primary effectiveness objective

\*Boundaries were calculated using EAST 6.4.1

In addition to reviewing the effectiveness data from the interim analyses, the DMC will be responsible for assessing the accumulating data on safety of the procedures during the study. The primary responsibility of the DMC is to safeguard the interests of study participants. The DMC also monitors the overall conduct of the clinical study. Further information regarding the DMC is found in Appendix C: Data Monitoring Committee.

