7.8. Interim Analyses

Two interim analyses are planned for the study. These analyses would be performed after 32 and 50 subjects have been randomized and completed their 6-month follow-up visits, respectively. Both the

sponsor and the DMC will assess the results of the interim analyses of the primary effectiveness objective and based on this assessment, the sponsor may decide to stop enrollment. However, while there are formally defined stopping rules for a successful primary effectiveness endpoint, there are no stopping rules for futility.

Patients randomized to the trial who have not reached 6-months of follow-up are not considered in assessing the primary effectiveness objective.

The time points of the analyses and criteria for study success are given in Table 1 below:

Table 2: Timing and Success Criteria for Interim and Final analyses

Time Point of Interim Analyses of the Primary Effectiveness Objective	Cumulative Alpha	Boundary*	Pass/Fail Primary Effectiveness Objective
After 32 subjects were randomized and completed their 6-month visit	0.01	0.01	If a two-sided p-value ≤ 0.01 , in favor of the treatment group, then the study passed the primary effectiveness objective
After 50 subjects were randomized and completed their 6-month visit	0.015	0.008	If a two-sided p-value ≤ 0.008 , in favor of the treatment group, then the study passed the primary effectiveness objective
Final Analysis: After 70 subjects were randomized and completed their 6-month visit	0.05	0.04	If a two-sided p-value ≤ 0.04 , in favor of the treatment group, then the study passed the primary effectiveness objective

*Boundaries were calculated using EaST 6.4.1, using the Survival Module.

In addition to reviewing the effectiveness data from the interim analyses, the DMC will be responsible for assessing the accumulating data on safety of the procedures during the study. The primary responsibility of the DMC is to safeguard the interests of study participants. The DMC also monitors the overall conduct of the clinical study. Further information regarding the DMC is found in Appendix C: Data Monitoring Committee.

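### The primary success rule is p < 0.05 in one section and p ≤ 0.04 at the final analysis in another; after two interim looks the 0.05 rule exceeds the promised 5% type I error

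*Protocol*

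**What the plan says.** Protocol 12.4.2 and SAP 7.10.2.2 give the same rule: if the hazard ratio is below one and "the two-sided log-rank p-value is less than 0.05, it will be concluded that" adding renal denervation raises chronic treatment success. Neither refers to interim looks or adjusted boundaries. The next paragraph of SAP 7.10.2.2 mentions the sample of 70 at the final analysis and again gives statistical significance as p below 0.05.

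On interim looks, protocol 12.8 says: "Two interim analysis of the primary effectiveness objective may be performed after 32 and 50 subjects have been randomized". Its table, repeated as SAP Table 2 in section 7.8, sets two-sided thresholds of 0.01 at the first look and 0.008 at the second. For the final analysis the SAP says: "If a two-sided p-value ≤ 0.04 , in favor of the treatment group, then the study passed the primary effectiveness objective".

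Protocol 12.4.6 commits to overall error control: "Any planned interim analyses will be constructed so that the overall Type I error of the study is no greater than 0.05". The EaST output in SAP section 6 gives critical values of 2.576, 2.611 and 2.049 at 14, 19 and 41 events, with cumulative alpha of 0.01, 0.015 and 0.05. SAP 7.5 says that no alpha adjustment will be made for multiple comparisons.

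**The concern.** The plan defines success on its only hypothesis test in two incompatible ways, and no text ranks them. They disagree for a final p-value above 0.04 and below 0.05. Taken literally, they also disagree for an interim p-value between 0.01 (first look) or 0.008 (second look) and 0.05.

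The 0.05 sentence looks like a survivor from the single-look design. The protocol's change history for version 16 lists 12.1, 12.4.6 and 12.8 as revised for the interim analyses, but not 12.4.2.

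Two things are at stake. First, using 0.05 at the end after spending alpha at two interims breaks the commitment in 12.4.6. Second, the sponsor sees the interim effectiveness results and may stop enrollment on them, so a success rule left open until then could be chosen with knowledge of the data.

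**Working it through.** **Inputs.** Events at the looks are 14, 19 and 41 (SAP EaST output), so the information fractions are t = 14/41 = 0.341, 19/41 = 0.463 and 1. The looks are actually triggered by patient counts, so the calculation was repeated at t = 32/70 = 0.457, 50/70 = 0.714 and 1. The hazard ratio is ln 0.75 / ln 0.50 = 0.415.

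**Method.** Under the null, B(t) = Z(t)·√t has independent normal increments with variance t_k − t_(k−1). Overall two-sided error is 1 − P(|Z1| < c1, |Z2| < c2, |Z3| < c3), where c = Φ⁻¹(1 − p/2) for a nominal threshold p. This was evaluated by recursive numerical integration.

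**Reproducing the plan.** Solving for cumulative alpha of 0.01, 0.015 and 0.05 at the event fractions gives critical values of 2.576, 2.611 and 2.049, the same as EaST. The final value corresponds to a nominal p of 0.0405. Under the alternative, the drift is |ln 0.415| × √(41/4) = 0.8795 × 3.2016 = 2.816. Incremental power is then 17.6%, 10.1% and 50.9%, total 78.6%, which matches SAP Table 1.

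**Comparing the rules.**

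| Thresholds (look 1 / look 2 / final) | Overall error, event fractions | Overall error, patient fractions |
|---|---|---|
| 0.01 / 0.008 / 0.04 (table) | 4.9% | 4.7% |
| 0.01 / 0.008 / 0.05 | 5.8% | 5.6% |
| EaST interim values, then 0.05 | 5.9% | 5.6% |
| 0.05 / 0.05 / 0.05 | 10.6% | 10.0% |

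A simulation of 20 million null paths at the event fractions gave 5.88% for the third row and 5.00% for the EaST boundaries.

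**If only one interim is done before a 0.05 final test.** First look only: 5.6% (event) or 5.5% (patient). Second look only: 5.4% or 5.1%. All exceed 5%.

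**Which rule the power belongs to.** Replacing 2.049 by 1.960 at the final look raises power to 17.6% + 10.1% + 53.3% = 81.0%. The stated 78.6% therefore corresponds to the final boundary near 0.04.

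**A side observation.** EaST's 2.611 at the second look is a nominal p of 0.0090, not the tabulated 0.008. The value 0.008 arises at the patient fractions (computed 0.0079). The tabulated value is the stricter one, so this does not inflate the error.

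**The case against.** The strongest reply is that the intended rule can be inferred. The tables have an explicit pass/fail column with a final-analysis row at 0.04, the EaST output agrees, and the power fits only that boundary. On this reading 0.05 is leftover wording or the overall level, and no sensible analyst would pass the first look at p = 0.03. This is persuasive about intent, and it makes the 10% to 10.6% figure a literal worst case. It does not remove the conflict: SAP 7.10.2.2 attaches 0.05 to a passage that names the final analysis, and SAP 7.5 could be cited in support of an unadjusted test.

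The excess is also small. At a 0.05 final look it is 0.6 to 0.9 points two-sided. Counting only false claims in favour of treatment, it is 2.8% to 2.9% against 2.5%. Small-sample behaviour of the log-rank test should not be charged to this conflict. Simulations with 70 subjects, under assumed null success rates and accrual periods, gave 4.7% to 5.5% for the 0.04 rule and 5.7% to 6.5% for the 0.05 rule. Even a single 0.05 test with no interims gave 5.1% to 5.5%.

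Protocol 12.8 says the interims may be performed, and with none the 0.05 rule would hold its nominal level. That is correct, but SAP 5.1 and 7.8 treat both as planned, and one look is already enough to exceed 5%.

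Finally, this is a feasibility study whose estimates are meant to be useful whether or not the test is significant. That lowers the consequences, but the plan itself chose formal alpha control.

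**Conclusion.** The concern holds. The two success rules contradict each other in the current text of both documents, and the one in the performance sections is wrong as written for a design with interim looks. Applied at the final analysis after the two planned looks, it gives an overall two-sided error of 5.6% to 5.9% against a commitment of no more than 5%. The tabulated thresholds give 4.7% to 4.9%.

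These figures assume that both interims are done at their tabulated or EaST thresholds, that the log-rank statistic is approximately normal with independent increments, and that information at the looks is close to the event or patient fractions used. The contradiction itself depends on none of these assumptions.

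**What to change.** In protocol 12.4.2 and SAP 7.10.2.2, replace the 0.05 criterion with a statement that success requires a hazard ratio below one and a two-sided log-rank p-value at or below the boundary for that analysis in the interim-analysis table, which is 0.04 at the final analysis. Align the later mention of significance at p below 0.05 in each section.

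Two short additions would close the remaining gaps. SAP 7.5 should say that it does not override the group-sequential boundaries. The interim section should say what final threshold applies if a planned look is skipped. Keeping 0.04 regardless is safe for type I error; with no looks at all and 41 events, power would be about 77.8% (at 0.0405) rather than 80.4% (at 0.05).

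The cost is a few sentences in each document, made before unblinded results are seen. Sample size and planned power do not change, because the 78.6% was computed under the boundary near 0.04. The only loss is that a final p-value above 0.04 and below 0.05 no longer counts as success.

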#### **12.4.3 Rationale for Performance Criteria**

In the STOP-AF trial, subjects randomized to receive cryoablation had a 6- month chronic treatment success rate of 75.0%. In the patient population of this feasibility study, including patients with either paroxysmal AF or persistent AF and with uncontrolled hypertension, the rate of chronic treatment success is expected to be lower. Also, use of intensive AF monitoring with the Reveal LINQ device has the potential to identify patients with recurrent AF that might not be detected with periodic trans-telephonic and Holter monitoring, as was performed in the STOP-AF trial, leading to a lower rate of chronic treatment success. In the treatment arm, the addition of the renal artery denervation procedure to the pulmonary vein isolation procedure for treatment of AF has the potential to increase the rate of chronic treatment success. While it's uncertain to what degree these factors may affect the rate of chronic treatment success, this feasibility study is designed to be able to identify a difference in chronic treatment success rate if the rate through 6 months is at least 75% in the Treatment arm and 50% in the Control arm through 6 months.

#### **12.4.4 Analysis Methods**

A log-rank test will be used to perform this hypothesis test. The log-rank test uses the time that each subject is free from chronic treatment failure, defined from the date of procedure to the date of chronic treatment failure, if it occurs, or latest of the following: a) the last follow-up visit date, or b) the last date on which AF was assessed, if chronic treatment failure does not occur during the subject's study follow-up. Subjects will be included through all available study follow-up.

In addition to the log-rank test, Kaplan-Meier curves will be used to estimate the rate of chronic treatment success. Cox proportional hazards regression will be used to estimate the hazard ratio and its 95% confidence interval between study arms.

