## 6.18 Scheduled in-office follow-up visits

### 6.18.1 One, Six and Every Six Month Visit Until Study Closure

It is recommended that anti-hypertensive medications and dose not be changed through the 6 month visit unless medically necessary. It is recommended that subjects be off all antiarrhythmic medications within 90 days post cryoablation procedure.

The following will be collected:

- blood and urine samples (not required after the 6 month visit)
- physical exam
- vital signs (including 3 blood pressure measurements according to Appendix G: Blood Pressure Measurement Procedures)
- review of medications
- assess for adverse events
- assess arrhythmias and symptoms, episodes of medical care suggestive of arrhythmia including hospitalizations, office or ER visits, or any AF-related procedures such as cardioversions or additional ablations
- interrogate the Reveal LINQ device, review prior CareLink reports and the current interrogation for possible AF related events

Alternative methods of data collection may be necessary in the case of extenuating circumstances, such as a global pandemic, when subjects are prohibited from coming into the office for required assessments. For all assessments completed via alternative methods in these circumstances, sites are not required to enter a protocol deviation for missing, alternative, and/or late data collection. Data unable to be collected remotely or via an alternative method should be collected at the next possible in-person visit.

In the event a subject is unable to return for an in-office follow-up visit, the alternative methods of obtaining follow-up assessments are listed below:

- In-home visit by trained and delegated site personnel or designee, i.e. home health care personnel. The following assessments may not be completed with an in-home visit:
  - CareLink in-office interrogation. Guide a subject through a full interrogation (“Interrogate All”) at the end of the follow-up visit
  - Renal Artery Imaging:
    - Make every effort to schedule in-person renal artery imaging as soon as possible.

When possible, subjects may be referred to a local imaging center for assessment. Local imaging technicians would require study training and delegation prior to assessment. In the event an in-home visit is not possible, the alternate methods for obtaining follow-up assessments are listed below:

- Virtual Visit, i.e. inclusive of video with study subject.

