### **6.20 System modification for Reveal LINQ**

A system modification will be reported in the event the Reveal LINQ requires invasive modification (e.g. reposition, explant, replacement). In the event of a system modification, the follow-up visit schedule for the subject will remain unchanged. If the device is explanted and a replacement will not be inserted, the subject should continue to stay in the study.

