## 6.23 Recurrence of atrial fibrillation

Documentation of AF recurrence must be provided to the sponsor and additional source documents may be requested. Documentation of AF must include the following:

- Reveal LINQ rhythm recording (EGM)

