## 6.24 Study exit

Contact the subject to review medications, adverse events, episodes of medical care suggestive of arrhythmia including hospitalizations, office or ER visits, and any AF-related procedures such as cardioversions or additional ablations. Have the subject manually transmit data from their Reveal LINQ device at study exit.

Subjects may be exited from the study for any of the following situations:

- Subject has completed follow-up
- Subject with LINQ battery at end of life, having completed at least 6 months of study follow-up
- Subject lost to follow-up
- Subject death
- Subject did not meet inclusion/exclusion criteria

- Subject not randomized
- Subject did not provide consent or data protection authorization
- Subject chooses to withdraw (e.g., consent withdrawal, relocation to another geographic location)
- Investigator deems withdrawal necessary (e.g. medically justified, inclusion/exclusion criteria not met, failure of subject to maintain adequate study compliance)

Once a subject is randomized, all efforts should be made to continue following the subject until study closure.

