### **12.4 Primary effectiveness objective**

The primary effectiveness objective compares the rate of chronic treatment success between study arms. Chronic treatment success is freedom from chronic treatment failure. Therefore, comparing the rate of chronic treatment success is equivalent to comparing the risk of chronic treatment failure.

Chronic treatment failure is defined as the occurrence of either

- 1) a documented episode of AF recorded on Reveal LINQ
- 2) an intervention for AF

occurring after a blanked follow-up period of 90 days from the study treatment procedure. AF episodes and repeat ablations that occur within 90 days of the study treatment procedure will not constitute chronic treatment failure.

Intervention for AF is defined as an invasive procedure intended for the definitive treatment of AF, including any ablation of the pulmonary veins or atrial triggers (other than protocol-specified ablation), interruption of AV nodal function, procedures to alter left atrial conduction or function such as the Maze procedure, or the implantation of an atrial pacemaker or atrial defibrillator; whether approved by relevant regulatory authorities or not for such indications; excluding electrical or pharmacologic cardioversion of arrhythmias and excluding procedures solely directed at the treatment of atrial flutter or atrial tachycardias.

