7.10.3.4. Analysis Methods

Kaplan-Meier curves will be used to estimate the rate of chronic treatment success for each study arm. Cox proportional hazards regression will be used to estimate the hazard ratio and its 95% confidence interval for the treatment effect between study arms. To support this analysis, a log-rank test will be used to determine if the freedom from chronic treatment failure rate differs between arms.

The Kaplan-Meier curves use the time that each subject is free from chronic treatment failure, defined from the date of procedure to the date of chronic treatment failure, if it occurs, or latest of the following: a) the last follow-up visit date, or b) the last date on which AF was assessed, if chronic treatment failure does not occur during the subject's study follow-up. Subjects will be included through all available study follow-up on or after the 6-month follow-up.

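### Subjects who keep attending after Reveal LINQ monitoring ends are credited with AF-free time in which AF cannot be recorded, so Kaplan-Meier success is overstated after the loss; how much depends on an unstated loss rate

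*Protocol*

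**What the plan says.** Protocol 12.4.4 measures event-free time for subjects without failure to the "latest of the following: a) the last follow-up visit date, or b) the last date on which AF was assessed" and uses all available follow-up. SAP 7.10.2.4 repeats the rule for the primary objective, and SAP 7.10.3.4 and 7.10.8.4 carry it to the secondary objective and ancillary objective 5, each ending in "the last date on which AF was assessed".

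Failure has two components (Protocol 12.4): "a documented episode of AF recorded on Reveal LINQ", or an invasive intervention for AF, in either case after the 90-day blanking period. Protocol 6.23 requires a LINQ recording as documentation of AF recurrence. Visits ask about "any AF-related procedures such as cardioversions or additional ablations" (Protocol 6.18.1), so they can find interventions without the device.

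Two provisions let follow-up outlast monitoring:
- Protocol 6.20: "If the device is explanted and a replacement will not be inserted, the subject should continue to stay in the study".
- Protocol 6.24 lists, among situations in which a subject may be exited, "Subject with LINQ battery at end of life, having completed at least 6 months of study follow-up". Exit is permitted, not required, and the same section says: "Once a subject is randomized, all efforts should be made to continue following the subject until study closure".

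**The concern.** A visit after LINQ monitoring has ended can show that no AF intervention took place. It cannot show freedom from AF as Protocol 12.4 defines it. The rule nevertheless moves the censoring date forward to that visit, and the subject stays in the risk set with the AF component switched off.

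This has two consequences. First, the arm-level success rates, which Protocol 12.4.2 offers as input to a pivotal design, are too high at times after the loss. Second, if loss is staggered over time and similar in both arms, the hazard ratio is pulled toward 1. Failures leave the Control risk set faster, so the share of unmonitored subjects grows faster there and the observed Control hazard falls more.

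The only other censoring rule, in SAP 7.4, covers subjects lost to follow-up. These subjects are still attending.

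**Working it through.** **Inputs from the documents.** Success at 6 months 50% Control and 75% Treatment, 1:1 allocation, 70 subjects, 16 months of accrual plus 6 of follow-up, dropout 5% per 6 months (Protocol 12.4.6). Looks at 14, 19 and 41 events with |Z| boundaries 2.576, 2.611 and 2.049 (SAP section 6). Expected timeline 51 + 6 months (Protocol 1.2). An existing LINQ needs at least 1 year of battery (Protocol 6.14).

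**The plan's own figure.** HR = ln(0.75)/ln(0.50) = 0.415. Exponential hazards with the stated accrual and dropout give 41.0 expected events at n = 69. A group-sequential normal calculation with information = events/4 gives 17.6% + 10.1% + 50.9% = 78.6% power, which matches SAP Table 1.

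**LINQ loss rate (assumption).** The documents give none. I used 1, 2, 5 and 10% per 6 months, equal in both arms and independent of AF. Attrition in Protocol 12.4.6 (about 1% expected, 5% planned) is a different quantity.

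**Six-month rate, loss from day 0.** With failure hazard l and loss hazard m, the rule estimates

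S_obs(t) = exp(-(l+m)t) + [m/(l+m)] × [1 - exp(-(l+m)t)].

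Control at 10% loss: 6l = ln 2 = 0.6931; 6m = -ln 0.9 = 0.1054; sum 0.7985; exp(-0.7985) = 0.450; 0.1054/0.7985 = 0.132; S_obs = 0.450 + 0.132 × 0.550 = 0.523, against a true 0.500. Treatment: 6l = 0.2877; sum 0.3930; S_obs = 0.675 + 0.268 × 0.325 = 0.762, against 0.750.

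| Assumed loss per 6 months | Subjects affected by month 6, of 70 (constant hazard) | Overstatement, Control/Treatment, points: constant hazard | Same, failures only after day 90 |
|---|---|---|---|
| 1% | 0.6 | 0.2/0.1 | 0.4/0.2 |
| 2% | 1.1 | 0.4/0.2 | 0.7/0.4 |
| 5% | 2.8 | 1.1/0.6 | 1.8/0.9 |
| 10% | 5.6 | 2.3/1.2 | 3.7/1.9 |

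For scale, the sampling standard error at 35 per arm is √(0.5 × 0.5/35) = 8.5 points in Control and √(0.75 × 0.25/35) = 7.3 in Treatment.

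**Power, loss from day 0.** Simulation with 20,000 trials per cell, a single look at p ≤ 0.04 and no other dropout. These levels are therefore not the plan's 78.6%; the comparison between rules is what matters. Each cell is LINQ-end censoring v current rule, in %.

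| Loss | 16+6, constant hazard | 51+6, constant hazard | 16+6, after day 90 | 51+6, after day 90 |
|---|---|---|---|---|
| 1% | 78.9 v 78.7 | 88.1 v 86.2 | 85.5 v 84.6 | 90.7 v 87.0 |
| 2% | 78.3 v 77.8 | 87.2 v 83.6 | 85.4 v 83.6 | 90.5 v 83.4 |
| 5% | 77.4 v 75.5 | 85.6 v 78.1 | 83.9 v 79.7 | 89.0 v 74.6 |
| 10% | 74.6 v 71.2 | 83.0 v 71.1 | 80.9 v 72.5 | 86.1 v 63.0 |

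Median HR at 10% loss with constant hazard is 0.414 v 0.429 (16+6) and 0.413 v 0.469 (51+6). With no true effect and equal loss, success is declared for Treatment in 1.9-2.4% of trials under both rules. If a quarter of unseen AF led to an intervention 3 months later, the 10% case (16+6, constant hazard) becomes 2.1/1.1 points and 74.9 v 72.7% power.

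**Late loss, from month 12, as for batteries.** No effect on the 6- or 12-month rates. At 10% per 6 months, power is 79.0 v 79.0% (16+6) and 87.4 v 86.0% (51+6); 24-month success is overstated by 1.4/2.1 points (51+6).

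**Tipping point (SAP 7.4).** Suppose LINQ monitoring ends at month 4 and the subject attends on day 185, inside the 180-194 window of Protocol Table 6, with no later visit. The censoring date becomes day 185. In a 6-month analysis the subject is not censored before the timepoint and is not converted. In the last pass, where every censored subject is converted, failure falls on day 186 instead of just after month 4.

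**The case against.** The strongest defence is that the visit date is a reasonable cut-off for half of the endpoint. Interventions are found at visits without the device, and any single cut-off for a composite with two sources of ascertainment is a compromise. That stands: the rule does not suit the AF-episode component, but it is not wrong for the composite as a whole.

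The affected group may also be very small. While the LINQ works, the two dates largely coincide. At battery end of life exit is allowed and a final transmission is requested. What mainly remains is explant without replacement in a subject who is still event-free and still attending. This stands too, and no document gives its frequency.

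The large power losses at 51+6 months rest on a hazard that never falls. Under it, 0.5^(57/6) = 0.1% of Control would be event-free at 57 months. If recurrences cluster early, those losses are smaller.

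Four stronger readings are tempting, and the documents do not support them:
- That the rule favours Treatment. This needs loss that differs by arm, and nothing in the documents suggests a difference or its direction.
- That battery depletion distorts the 6-month rate. The 1-year minimum for existing devices argues against it.
- That SAP 7.4 leaves these subjects out altogether. Its last pass converts all censored subjects, and its list of sensitivity analyses is open-ended. The weakness is the date at which they fail, and the gap at 6 months.
- That a missed monthly transmission is lost monitoring. It is not in itself, if the device data are retrieved later.

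**Conclusion.** The point holds and is worth correcting, but it is not critical. As written, the rule credits AF-free time in which AF cannot be recorded, and no planned analysis fully repairs this. The direction is clear: Kaplan-Meier success errs upward after the loss and, with similar and staggered loss in both arms, the hazard ratio errs toward 1. If every subject lost monitoring at the same follow-up time, the hazard ratio would not change.

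The size is unknown because the loss rate is. At 1-2% early loss the 6-month effect is negligible beside sampling error. At 10% it reaches about 1-2 points with constant hazard, or 2-4 if failures start after day 90. The power cost is modest under the design timeline at low loss. It is larger only with frequent early loss or with long follow-up at a sustained hazard. Late battery loss matters little.

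**What to change.** 1. In Protocol 12.4.4 and SAP 7.10.2.4, 7.10.3.4 and 7.10.8.4, censor event-free subjects at the last date of valid LINQ monitoring. SAP 7.10.9.3 already derives an end date of this kind for AF burden. It assumes uninterrupted recording, so it needs adjusting for unmonitored gaps such as explant followed by later replacement.
2. In Protocol 12.4 and SAP 7.10.2.3, state one rule for AF interventions after that date, so that events and event-free time beyond it are treated alike.
3. Prespecify three sensitivity analyses: the current rule; post-LINQ interventions counted as failures; and a tipping point in which subjects whose monitoring ended early fail from their last LINQ date.
4. Report LINQ loss by arm: number, date and reason.

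The sponsor sees interim effectiveness results (Protocol 12.8, SAP 7.8), and the documents do not say whether a look has taken place. If the sponsor would rather not change the primary rule after one, it can keep the rule and prespecify LINQ-end censoring as a sensitivity analysis, with item 4 unchanged.

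The cost is wording in four analysis sections, a matching endpoint sentence, one listing and three extra runs. If the change is judged a principal feature, Protocol 12.2 requires an amendment, with the approvals in Protocol section 4. The downside is slightly less follow-up, no time contributed by a subject without LINQ data, and, if the primary rule changes, a few late interventions that count only in the sensitivity analysis.
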